6.2. Number of Participants

Approximately 10,000 participants will be randomized at approximately 750 investigational centers in 20-25 countries. Approximately 20% of participants will be women.

6.3. Treatment Assignment

All participants who successfully complete the 21-day Placebo Run-In Period with ≥ 75% adherence to placebo tablets will be eligible for randomization to pemafibrate or placebo at the Randomization Visit (Visit 2). Participants who meet all inclusion criteria and none of the exclusion criteria will be randomized in a 1:1 ratio to study drug by the responsible site investigator using an interactive computer system. The randomization process will involve stratification by sex, prior history of CVD (primary vs. secondary prevention cohorts), and statin use at baseline, defined as those who are taking no statin at baseline or are statin intolerant compared to all others. There will be recruitment caps such that no more than one-third of the study population will consist of participants without prior CVD (primary prevention cohort).

6.4. Study Drug Dose Adjustment Criteria

Not applicable.

6.5. Study Withdrawal

6.5.1. Overall Study Termination

The closeout phase of the study will be initiated when approximately 1,304 adjudicated and confirmed primary endpoints have accrued with a minimum of 200 events in women, or in accordance with DSMB recommendations, should there be evidence of futility or excess harm to participants. In addition, if in the opinion of the Sponsor, the clinical observations in the study suggest it may be unwise to continue, the study may be terminated. In addition, the Sponsor may terminate the study at any time.

6.5.2. Study Termination at Investigational Sites

If it becomes apparent that participant enrollment at a specific investigational site is unsatisfactory with respect to quality or quantity, or data recording is repeatedly inaccurate or incomplete, the Sponsor has the right to terminate the study and remove all study materials from that investigational site. A written statement will be provided to the investigator, the IRB/IEC/REC, and regulatory authorities, if required. In the event of any serious or non-serious AE(s) having occurred at a site, all documentation relating to the event(s) must be obtained.

7. SELECTION AND WITHDRAWAL OF PARTICIPANTS

Study participants will be adult men and women with T2D and who are at high risk (primary prevention cohort; one-third of randomized participants) or very high risk (secondary prevention cohort; two-thirds of randomized participants) of incurring a major CVD event based on study inclusion criteria.

7.1. Participant Inclusion Criteria

Participants must meet all of the following criteria for enrollment into the study:

- 1. Fasting TG ≥ 200 mg/dL (2.26 mmol/L) and < 500 mg/dL (5.65 mmol/L) at Visit 1 (Screening/Enrollment Visit) or Visit 1.1 (Retest)
- 2. HDL-C ≤ 40 mg/dL (1.03 mmol/L) at Visit 1 (Screening/Enrollment Visit) or Visit 1.1 (Retest)
- 3. Type 2 diabetes of longer than 12 weeks duration documented in medical records, for example: local laboratory evidence through medical record review of elevated HbA1c (≥ 6.5% [48 mmol/mol]), elevated plasma glucose (fasting ≥ 126 mg/dL [7.0 mmol/L]), 2-hour ≥ 200 mg/dL [11.1 mmol/L] during oral glucose tolerance testing, or random value ≥ 200 mg/dL with classic symptoms, or currently taking medication for treatment of diabetes; AND either
 - a) Age \geq 50 years if male or \geq 55 years if female (primary prevention cohort), OR
 - b) Age ≥ 18 years and established systemic atherosclerosis (secondary prevention cohort), defined as any 1 of the following:
 - i. Prior MI or ischemic (non-hemorrhagic) stroke
 - ii. Coronary angiographic lesion of $\geq 60\%$ stenosis in a major epicardial vessel or $\geq 50\%$ left main stenosis
 - iii. Asymptomatic carotid disease with $\geq 70\%$ carotid artery stenosis
 - iv. Symptomatic carotid disease with $\geq 50\%$ carotid artery stenosis
 - v. Symptomatic lower extremity PAD (ie, intermittent claudication, rest pain, lower extremity ischemic ulceration, or major amputation with either ankle-brachial index ≤ 0.9 or other diagnostic testing [toe-brachial index, angiogram, or other imaging study])
 - vi. Prior arterial revascularization procedure (including coronary, carotid, or peripheral angioplasty/stenting, bypass, or atherectomy/endarterectomy)
- 4. In addition, by Visit 1 (Screening/Enrollment Visit), participants must be either:

- a) Receiving treatment with a stable dose (ie, for at least 12 weeks) of a qualifying moderate- to high-intensity statin (atorvastatin ≥ 40 mg/day, rosuvastatin ≥ 20 mg/day, simvastatin ≥ 40 mg/day*, or pitavastatin 4 mg/day); or
- b) Have evidence of LDL-C \leq 70 mg/dL (1.81 mmol/L) by local laboratory determination within the previous 12 months[#], or
- c) Statin intolerant⁺ and have evidence of LDL-C ≤ 100 mg/dL (2.59 mmol/L) by local laboratory determination within the previous 12 months.

- [#] If untreated or on stable dosing (ie, for at least 12 weeks) of another lipid-lowering regimen that may include a statin with or without ezetimibe and/or a PCSK9 inhibitor.
- ⁺ Statin intolerance is defined as: the inability to tolerate at least 2 statins: 1 statin at the lowest daily starting dose (defined as rosuvastatin 5 mg, atorvastatin 10 mg, simvastatin 10 mg, lovastatin 20 mg, pravastatin 40 mg, fluvastatin 40 mg or pitavastatin 2 mg), AND another statin at any dose, due to skeletal muscle-related symptoms, other than those due to strain or trauma, such as pain, aches, weakness, or cramping, that begins or increases during statin therapy and stops when statin therapy is discontinued. Participants not receiving a daily regimen of a statin (eg, 1-3 times weekly) could also be considered "statin intolerant" if they cannot tolerate a cumulative weekly statin dose of 7 times the lowest approved tablet size, and the criteria outlined above are also met.
- 5. Ability to understand and comply with study procedures and give written informed consent.

7.2. Participant Exclusion Criteria

Presence of exclusionary criteria will be assessed at the Screening/Enrollment Visit (Visit 1), which is then followed by a 21-day Placebo Run-In Period preceding randomization into the study. Participants are excluded from participation if any of the following criteria apply:

- 1. Current or planned use of fibrates or agents with PPAR-α agonist activity (eg, saroglitazar) within 6 weeks (42 days) of Visit 1 (Screening/Enrollment Visit). Note: PPAR-γ agonists (eg, glitazones such as pioglitazone and rosiglitazone) are allowed
- 2. Known sensitivity to PPAR-α agonists or tablet excipients
- 3. Initiation of, or change in, current TG-lowering therapy within 12 weeks of Visit 1 (if applicable). Note: TG-lowering therapy is defined as niacin > 100 mg/day or dietary supplements or prescription omega-3 fatty acids > 1 g/day
- 4. Type 1 diabetes mellitus
- 5. Uncontrolled diabetes mellitus as defined by a HbA1c > 9.5% [80 mmol/mol] at Visit 1 (Screening/Enrollment Visit)

^{*} Participants enrolled on simvastatin > 40 mg/day must have been taking and tolerating that dose for at least 12 months.

Version 3 dated 18-Mar-2020

- 6. Untreated or inadequately treated hypothyroidism [thyroid stimulating hormone (TSH) > 2.0 X the ULN or Free T4 ≤ the lower limit of normal] or hyperthyroidism; controlled thyroid disease (permitted) requires normal TSH and stable therapy for at least 4 weeks
- 7. Recent CVD event (eg, MI or stroke) within 8 weeks of Visit 2 (Randomization Visit)
- 8. Recent or planned vascular intervention within 8 weeks of Visit 2 (Randomization Visit)
- 9. New York Heart Association Class IV HF
- 10. Known homozygous familial hypercholesterolemia (heterozygous is permitted) or familial hypoalphalipoproteinemia
- 11. Documented previous occurrence of myositis/myopathy
- 12. Unexplained CK > 5 X ULN
- 13. Liver disease defined as cirrhosis or Child-Pugh class B and C, or ALT or AST > 3 X ULN
- 14. Biliary obstruction or hyperbilirubinemia (ie, total bilirubin > 2 X ULN, except with a documented diagnosis of Gilbert's disease)
- 15. Chronic renal insufficiency, defined by an eGFR < 30 mL/min/1.73 m² by the Chronic Kidney Disease Epidemiology Collaboration (CKD-EPI) formula or kidney transplant, regardless of renal function
- 16. Unexplained anemia (hematocrit $\leq 30\%$)
- 17. Uncontrolled hypertension (seated systolic blood pressure > 160 mmHg and/or diastolic blood pressure > 100 mmHg) at Visit 2 (Randomization Visit)
- 18. History of chronic active hepatitis B or hepatitis C, or known infection with human immunodeficiency virus (HIV); participants with documented hepatitis C resolution after treatment are permitted
- 19. Active malignancy, except non-melanoma skin cancer or carcinoma in situ of the cervix, within the last 2 years
- 20. Prior organ transplant or any condition likely to lead to organ transplantation in the next 5 years
- 21. Current or anticipated chronic use of cyclosporine, rifampicin, or other inhibitors of organic anion transporting polypeptides (OATP)1B1, or OATP1B3
- 22. History of alcoholism or unwillingness to limit alcohol intake to < 15 alcoholic beverages (or units) per week or < 5 alcoholic beverages (or units) during a single occasion for men and < 8 alcoholic beverages (or units) per week or < 4 alcoholic beverages (or units)

during a single occasion for women during the study period. Note: One alcoholic beverage (unit) is defined as 12 oz. (350 mL) of beer, 5 oz. (150 mL) of wine, or 1.5 oz. (45 mL) of liquor

- 23. History of hereditary problems of galactose intolerance, Lapp lactase deficiency, or glucose-galactose malabsorption
- 24. Women who are pregnant, lactating, planning to be pregnant or lactating during the study period, or WOCP who are not using an acceptable method of contraception

WOCP are adult females who are sexually active with a non-sterilized male partner unless she meets 1 of the following criteria as documented by the investigator:

- history of hysterectomy or tubal ligation prior to signing the informed consent form (ICF); or
- menopause, defined as either a) age > 50 years old and ≥ 1 year since last menstrual period or documented follicle-stimulating hormone (FSH) level in the post-menopausal range or b) for women ≤ 50 years old, ≥ 2 years since her last menstrual period without an alternative medical cause, and documented FSH level in the post-menopausal range

To be eligible, WOCP must have a negative pregnancy test at Visit 1 (Screening/Enrollment Visit) and agree to use an adequate method of contraception during the study and for 1 additional menstrual cycle following the final study visit. Adequate methods of contraception for WOCP include: oral, implanted or injectable contraceptive hormones; mechanical products (eg, intrauterine device [IUD]); or barrier methods (eg, diaphragm, condoms, cervical cap) with spermicide. Local regulatory authorities or IRB/IEC/REC may impose additional restrictions on acceptable contraceptive methods which must be applied by relevant sites and be documented in the investigator study documents. The participant's understanding of the contraceptive requirements must be documented by the investigator.

- 25. A medical condition, other than vascular disease, with life expectancy < 3 years, which might prevent the participant from completing the study
- 26. Any factors likely to limit adherence to the study medications and procedures, such as substance abuse, dementia, plans to move within the next 2 years, and/or history of noncompliance with medication or scheduled appointments, and
- 27. Participation in another clinical study at the time of informed consent, or has received an investigational drug within 90 days before signing the informed consent for this study.

Participants with uncontrolled diabetes, uncontrolled hypertension, uncontrolled thyroid disease, recent CVD event or revascularization procedure, or other medical instability due to an intervening medical condition may be re-evaluated for re-screening at the investigator's discretion once remedies have been instituted and the participant is stable for least 4 weeks

Version 3 dated 18-Mar-2020

(28 days) at the time of the repeat Pre-Screening Visit (Visit 0). Re-screening may occur on a one-time basis only and should occur after a discussion with the Medical Monitor.

7.3. Study Drug Discontinuation

Participants who discontinue study drug are not required to withdraw from the study and should continue all in-person visits and telephone contacts to monitor for AEs and the occurrence of potential endpoint events until the CSED Visit. At a minimum, vital signs should be obtained at in-person visits, but blood draws are at the investigator's discretion until the participant resumes study drug.

It will be necessary to make a distinction between participants who prematurely discontinue study drug treatment and those who withdraw from the study. All study drug discontinuations should be considered temporary interruptions because participants are allowed to restart medication at any time if the condition leading to study drug interruption has resolved, eg, a woman who becomes pregnant while in the study can resume study drug when she is no longer pregnant or breastfeeding. If a participant has discontinued study drug and the investigator has determined that it is appropriate to re-start study drug, then at the investigator's discretion and with prior approval of either the Sponsor or medical monitor, the investigator may elect to re-start the participant on a once a day dose of study drug with the goal of achieving twice daily dosing.

If the participant discontinues study drug, the reason should be captured and could include the following:

- 1. The participant meets any of the criteria specified in Section 7.3.1
- 2. The participant begins to take any medication(s) that is contraindicated by the protocol
- 3. The participant develops an AE that, in the opinion of the investigator, would compromise the participant's safety to continue the study drug
- 4. The participant becomes pregnant
- 5. The participant withdraws consent
- 6. The participant requests discontinuation of the study drug for any reason, or
- 7. In the investigator's judgment, it is in the participant's best interest

Although a participant is not obligated to give his/her reason for discontinuing study drug, the investigator will make a reasonable effort to obtain the reason while fully respecting the participant's rights. Unless revoked, further contact in the case of withdrawal from the study will occur consistent with methods listed in the informed consent form. The reason for discontinuation of study drug must be documented in the electronic case report form (eCRF). The Clinical Study Report (CSR) will include the reason(s) for discontinuation of study drug.

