7.3.1. Study Drug Discontinuation Criteria for Persistent Abnormal Clinical Laboratory Values

If at any time during the study a participant develops elevations in ALT or AST > 3 X ULN, or CK > 5 X ULN, the study site will receive an alert from the central laboratory.

Study drug should be discontinued immediately and permanently when any of the following criteria are met*:

- ALT or AST > 8 X ULN
- ALT or AST > 3 X ULN with bilirubin > 2 X ULN
- ALT or AST > 3 X ULN with the appearance of fatigue, nausea, vomiting, right upper quadrant pain or tenderness, fever, rash, and/or eosinophilia (> 5%)
- Rhabdomyolysis regardless of CK value

Study drug should be discontinued temporarily and requires repeating laboratory testing when any of the following criteria are met*:

- ALT or AST > 3 X ULN
- CK > 10 X ULN

Participants should undergo repeat laboratory measurements as soon as possible, within 72 hours (unless otherwise specified). Repeat laboratory measurements will include those tests outlined in Section 12.1.2.2.1 and Section 12.1.2.2.2. Local laboratory measurements may be used to facilitate follow-up.

If the repeat ALT or AST is > 3 X ULN with International Normalized Ratio (INR) > 1.5, study drug should be discontinued permanently. If the INR is < 1.5 but the ALT or AST is > 5 X ULN and persists beyond 2 weeks, study drug should be discontinued permanently. If the ALT or AST values recover without meeting the discontinuation criteria, study drug can be resumed at the investigator's discretion.

For CK > 10 X ULN, if the repeat CK elevation remains > 5 X ULN and is not explained by exercise or trauma, study drug should be discontinued permanently. If the CK elevation remains > 5 X ULN and is explained by exercise or trauma, the patient may continue therapy and be followed until they have returned to baseline, or the investigator considers them clinically stable. If exercise- or trauma-related elevation does not resolve, the study drug should be discontinued permanently. If the CK values recover without meeting the discontinuation criteria, study drug can be resumed at the investigator's discretion.

^{*}Participants who discontinue study drug are not required to withdraw from the study and should continue all in-person visits and telephone contacts to monitor for AEs and the occurrence of potential endpoint events until the CSED Visit.

Study drug can be continued, but requires repeating laboratory testing when the following criterion is met:

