• CK > 5 X ULN but < 10 X ULN

Participants should undergo repeat laboratory measurements as soon as possible, within 72 hours (unless otherwise specified). Repeat laboratory measurements will include those tests outlined in Section 12.1.2.2.2. Local laboratory measurements may be used to facilitate follow-up.

If the CK elevation remains > 5 X ULN and is not explained by exercise or trauma, study drug should be discontinued permanently. If the CK elevation remains > 5 X ULN and is explained by exercise or trauma, the patient may continue therapy and be followed at least weekly until CK values fall below 5 X ULN, at which time the study drug may be resumed by the investigator. If exercise- or trauma-related elevation does not resolve, the study drug should be discontinued permanently.

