8.3. Treatment Compliance

At each in-person visit, participants will be reminded by the sites of the importance of adhering to their treatment regimen for the entire duration of the study. Any interruptions of therapy should be as brief as possible and only for clinically-indicated reasons, such as AEs. Study medication can be re-started at any time in participants willing to resume treatment. Discontinuations will be discouraged and should be based on compelling clinical reasons.

For every participant, an assessment of compliance with study drug must be obtained at each scheduled in-person visit where study drug is dispensed and unused study drug returned. Compliance is defined as $\geq 75\%$ for the Placebo Run-In Period and $\geq 80\%$ during the treatment period.

Study medication will be dispensed in amounts exceeding the amount required until the next scheduled study visit. Participants will be instructed to return all unused study medication at the next visit. Compliance to the study drug regimen will be evaluated by tablet count of unused tablets and will be documented in the eCRF. If compliance falls below 80% during the post-randomization period, the investigator or designee will assess potential factors leading to the lack of compliance and counsel the participant. At the end of the study, the final study drug compliance will be calculated by unused tablet count.

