9.5. Study Drug Administration

Participants will self-administer their assigned study drug daily over the course of the study treatment period. Participants will take an oral dose of pemafibrate 0.2 mg or matching placebo tablet twice daily starting the day after completion of Visit 2. Participants may take the study drug in either a fed or fasted state (before or after meals); however, participants should be instructed by the sites to try and remain consistent with the time of dosing for all doses throughout the study. Participants will be instructed by the site to follow dosing instructions on the drug packaging, and to return all remaining unused study drug and packages at the next visit.

Participants will be asked whether there have been any problems with taking the medication, and the investigator will record any significant departure from the dosing instructions (eg, misuse or overdose) as a protocol deviation. For each participant, the number of tablets dispensed, taken, and returned will be recorded on the site's Drug Accountability Log and recorded in the eCRF. Participant compliance will be assessed from information recorded in the eCRF, including study drug count and the start and end date of therapy. Participants will be considered compliant if they have taken $\geq 75\%$ and $\geq 80\%$ of the intended regimen during Placebo Run-In and Treatment Periods, respectively.

Confidential K-877-302 Study Protocol

Version 3 dated 18-Mar-2020

During the active treatment period, if compliance is < 80%, the participant will be counseled by the site on the importance of compliance with the study drug administration.

If a participant has discontinued study drug and the investigator has determined that it is appropriate to re-start study drug, then at the investigator's discretion and with prior approval of either the Sponsor or medical monitor, the investigator may elect to re-start the participant on a once a day dose of study drug with the goal of achieving twice daily dosing.

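### Protocol Section 7.3 classes every study drug stop as temporary while Section 7.3.1 makes some permanent, and no stated rule governs restart once the abnormality has resolved

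*Protocol*

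**What the plan says.** Protocol Section 7.3 first separates stopping study drug from leaving the study. It then states: "All study drug discontinuations should be considered temporary interruptions because participants are allowed to restart medication at any time", with the condition "if the condition leading to study drug interruption has resolved" and pregnancy as its example. Its list of reasons for stopping opens with "The participant meets any of the criteria specified in Section 7.3.1".

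Two other passages deal with restart. Section 8.3, on compliance, says: "Study medication can be re-started at any time in participants willing to resume treatment". Section 9.5 repeats a sentence from 7.3. Where the investigator has judged restart appropriate, and with prior approval from the sponsor or the medical monitor, "the investigator may elect to re-start the participant on a once a day dose of study drug", working back towards twice-daily dosing. Neither section excepts Section 7.3.1 cases.

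Section 7.3.1 sorts laboratory findings into permanent stop, temporary stop, and continue with retesting. Its first list reads: "Study drug should be discontinued immediately and permanently when any of the following criteria are met". The entries are:

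- a transaminase (ALT or AST) above 8 X ULN;
- a transaminase above 3 X ULN together with bilirubin above 2 X ULN;
- a transaminase above 3 X ULN accompanied by listed symptoms or eosinophilia;
- rhabdomyolysis at any CK value.

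Permanent stops also follow from repeat tests: ALT or AST > 3 X ULN with INR > 1.5, ALT or AST > 5 X ULN persisting beyond 2 weeks at a lower INR, and a CK that stays > 5 X ULN. On the last, the text is that if the elevation "is not explained by exercise or trauma, study drug should be discontinued permanently". An elevation attributed to exercise or trauma that fails to resolve is also a permanent stop.

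On resumption, Section 7.3.1 says: "If the ALT or AST values recover without meeting the discontinuation criteria, study drug can be resumed", at the investigator's discretion. A parallel sentence covers CK > 10 X ULN.

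**The concern.** The general rule covers all stops and expressly takes in the Section 7.3.1 criteria. The subsection then makes some of those same stops permanent. A site asked to restart someone whose laboratory values have returned to normal can find text supporting either answer.

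The stake is mainly participant safety, because these criteria guard against risks that the protocol itself singles out. The liver is named as the primary target organ of toxicity in nonclinical work (Section 4.7.1). Rhabdomyolysis with a co-administered statin is described as a risk that cannot be excluded (Section 4.8). Muscle events and liver disease are the adverse events of special interest (Section 12.2.7).

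There is a smaller consequence for the data. If every stop is temporary, it is unclear when a stop should be recorded as a withdrawal of drug.

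**Working it through.** No arithmetic applies and the plan has no figure to reproduce. The check is to read the passages against each other.

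**1. Does the general rule reach Section 7.3.1 cases?** Yes. Section 7.3 speaks of all discontinuations and lists the 7.3.1 criteria as its first reason. It is not confined to optional stops either: its own example is pregnancy, for which Section 12.2.8 makes stopping drug mandatory.

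**2. Does the condition that the cause has resolved remove the conflict?** It narrows it. A laboratory abnormality can resolve, and the condition is then met. Section 8.3 does not carry the condition at all.

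**3. Test cases.**

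| Participant | Section 7.3 | Section 7.3.1 | Result |
|---|---|---|---|
| ALT > 3 X ULN, recovers, no permanent criterion met | Temporary; restart allowed | Temporary; may resume at investigator's discretion | Agree |
| ALT > 8 X ULN, not resolved | Labelled temporary, but restart condition not met | Permanent | Same action, different label |
| ALT > 8 X ULN, later normal | Temporary; restart allowed | Permanent | Conflict |
| CK > 10 X ULN, repeat > 5 X ULN and not attributed to exercise or trauma, later normal | Temporary; restart allowed | Permanent | Conflict |
| Rhabdomyolysis, later resolved | Temporary; restart allowed | Permanent | Conflict |

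The instructions on restart diverge between 7.3 and 7.3.1 only where a permanent criterion was met and the abnormality then resolved.

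**4. Does the other restart text settle it?** No. Section 8.3 has no exception for 7.3.1 and no approval step. The prior approval in Sections 7.3 and 9.5 is attached, as written, to restart on a once-daily dose. It may work as a check in practice, but it is not worded as a general safeguard and does not refer to 7.3.1.

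**5. What is affected in the analysis?**

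- The primary analysis uses the randomized group regardless of adherence (Protocol 14.4, SAP 6.4.3). No alpha, power or event-count input depends on these passages.
- Retrieved dropouts are participants who are no longer taking drug but are still followed (Protocol 14.5, SAP 8.5). That is actual drug status, not a temporary or permanent label.
- SAP 10.1 counts interruption and discontinuation together, so the label does not matter there. SAP 10.2.2 tabulates premature discontinuation for adverse events separately, so the label could matter there. The effect is descriptive.

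**The case against.** The strongest reply is that the specific rule is understood to override the general one. Section 7.3.1 sits under 7.3. For ALT/AST and for CK > 10 X ULN, its resumption sentences leave out exactly the participant in question, the one who recovered after meeting a discontinuation criterion. Sections 12.1.2.2.1 and 12.1.2.2.2 send sites to 7.3.1 for liver and CK elevations, so a site handling an alert would be reading that subsection. The sentence in 7.3 serves retention, since it follows directly on the distinction between stopping drug and leaving the study, and Section 8.3 is a compliance section. This has real force and makes an actual wrong restart less likely. It remains an inference, because no order of precedence is stated and the general sentence takes in the 7.3.1 criteria by name.

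Some stronger readings do not stand:

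- **That Section 7.3 permits unconditional restart, or directs it.** It requires that the cause has resolved, and its once-daily restart provision presupposes the investigator's judgment that restart is appropriate.
- **That the eCRF cannot tell the cases apart.** Section 7.3 already requires the reason for stopping to be documented, and Section 12.2.4 already separates *Drug interrupted* from *Drug withdrawn*. What is missing is a rule for when each applies.
- **That the imputation analyses are compromised.** Retrieved-dropout status would change only if someone were actually restarted.

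**Conclusion.** The inconsistency is real and narrow. Sections 7.3, 8.3 and 9.5 on one side and Section 7.3.1 on the other do not give a single answer on restart for a participant who met a permanent 7.3.1 criterion and whose abnormality later resolved. The temporary criteria in 7.3.1 agree with 7.3.

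The documents do not give the number affected. A reader might infer that the problem extends to every participant meeting a permanent criterion across the roughly 750 centers. That does not follow, because 750 is the planned number of sites and the divergence on restart needs both resolution and a restart being considered. The number is probably small. Section 4.7.2 describes ALT or AST elevations of at least 5 X ULN as infrequent, and Section 4.8 says rhabdomyolysis had not been reported with pemafibrate. That judgment assumes the earlier experience, up to 52 weeks in Section 4.8, carries over to treatment of up to 5 years. It is also less direct for the permanent criteria set at > 3 X ULN with bilirubin, symptoms or INR.

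The primary test, its power and its alpha are unaffected. This is a defect in operating instructions on a safety matter. It should be corrected, but it does not threaten the trial's inference.

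**What to change.** Reconcile Sections 7.3, 7.3.1, 8.3 and 9.5 so that one stated rule governs restart after a permanent 7.3.1 criterion has been met, including when the abnormality later resolves. The other sections can then cross-refer to it. Which clinical rule that should be is for the sponsor and its medical advisers.

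Align the existing eCRF entries with that rule: state when *Drug interrupted* and when *Drug withdrawn* applies, and how a permanent 7.3.1 stop is entered as a reason for discontinuation. No new data collection is needed.

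The cost is a clarification letter or amendment wording, plus a line in the eCRF completion guidelines. If treatment has already ended, new wording can no longer guide sites. The sponsor should then identify and report any participant restarted after meeting a permanent criterion.
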